Parkinson's disease is a neurodegenerative disease that results in various deficits, including cognitive impairments, for which there is a lack of interventions. Improvisational dance (ID) is spontaneously generated movement, similar to how one moves in everyday life. ID requires the integration of cognitive capacities to execute movements, and thus may strengthen cognitive processes involved in daily life function. ID has been shown to improve motor function in people with PD. The purpose of this study is to understand the effects of ID on cognition and daily function for people with PD. Specifically, it will test the effect of IMPROVment®, a method of ID designed for people with PD, on cognition and daily function. We will conduct a quasi-randomized wait-list controlled trial. Participants will be recruited and screened for eligibility through the St. Louis Chapter American Parkinson's Disease Association. Inclusion criteria includes: 50 years or older, PD diagnosis (mild to moderate), follows simple verbal cues, walks at least 3 meters independently, no contraindications in physical activity, mild cognitive impairment (determined by MOCA score), and no diagnosis of other severe comorbidities. The target sample size is 15-20 participants. Once enrolled, participants will undergo baseline testing (T1). Then participants will be randomly assigned to one of two groups: ID or waitlist control (WC). Participants in the ID group will begin a 12-week intervention where the group will meet once a week for a 1-hour IMPROVment® class. Participants in the WC group will continue with their regular routine for 12 weeks. After 12 weeks, all participants will complete Time 2 testing (T2; primary endpoint). Then WC participants will participate in the same IMPROVment® class for the following 12 weeks followed by Time 3 testing (T3; exploratory endpoint). For primary analysis, assessment scores will be compared across time point (T1, T2) and group (ID, WC) using mixed model ANOVA. Our results will provide further information on the effects of the IMPROVment® method for people with PD.

A2 Primary Hypothesis

The *central hypothesis* is that engagement in an improvisational dance (ID) class will benefit cognition and daily function among people with PD.

A3 Purpose of the Study Protocol

The purpose of this study protocol is to detail the various aspects of this study.

B Background

B1 Prior Literature and Studies

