Participants will be recruited and screened for eligibility through the St. Louis Chapter American Parkinson's Disease Association (APDA). Approximately 15-20 participants diagnosed with PD will be recruited for this study. Consent will be obtained from each participant by select members of the research team. Each participant will be walked through the informed consent document in detail and allowed to ask questions with no cohesion. Participants will be re-assented to additional research processes after 9.24.2019 upon IRB reapproval.

2.d Randomization Method and Blinding

After consent is given and T1 testing is completed, participants will be randomly assigned (coin flip) to either participate immediately (i.e., starting the next week) in 12-weeks of IMPROVment (ID group) or to continue with regular routine for 12 weeks before starting IMPROVment (WC group). Once we reach 10 participants in a group, remaining participants will be assigned to the other group. In addition, if the participant would like to be a part of this study, but can only participate in one group or the other, we will try to accommodate his/her needs.

2.e Risks and Benefits

Risks:

Participation in this study could result in the following risks. In addition to these, there may be other unknown risks, or risks that we did not anticipate, associated with being in this study.

One risk of participating in this study is that confidential information about participants may be accidentally disclosed. We will use our best efforts to keep the information about participants secure.

Another risk of participating in this study is an increased risk for falls. Although we do not expect the participants to fall during the intervention, precautionary measures are in place to decrease this risk (i.e. certified therapist present at all times, OT students monitoring the participants, movement modifications sitting in a chair).

Benefits:

Participants will not directly benefit from being in this study. Participants may indirectly benefit from participating in this study with the increased social participation and entertaining nature of the study program.

However, we hope that, in the future, other people might benefit from this study because it will help to provide information on how people with PD can best learn and remember in their daily lives.

2.f When and How to Withdraw Subjects

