See Adverse Event Reporting Form in Appendix 3. Data on the number and type of adverse events will be collected and reported when study results are disseminated.

4.f Reporting Procedures

See Adverse Event Reporting Form in Appendix 3.

4.g Adverse Event Reporting Period

Adverse events will be reported to the PI immediately (within one day), and the participant will be encouraged to report them to his/her primary care physician or neurologist within the week.

4.h Post-study Adverse Event

NA

G Statistical Plan

G1 Sample Size Determination and Power

Each group will have 7-10 participants, a typical size for ID classes. This ensures enough participants to create a cohesive group, but also to provide an appropriate level of safety. Since this is a pilot study, power analyses were not conducted. Rather, data from this study can be used to power future studies. Although attrition is not anticipated, we aim to recruit 10 participants per group to ensure there are at least 7 participants in the class.

G2 Interim Monitoring and Early Stopping

NA

G3 Analysis Plan

Aim 1: Investigate the effects of IMPROVment® on cognition for people with PD.
Cognition will be assessed at pre (T1) and post (T2) using the NIH (CB), AUT, and WCPA. Scores obtained in these assessments will be compared across time point and group using mixed model ANOVA.

Aim 2: Investigate the effects of IMPROVment® on daily functions for people with PD.
Daily function will be measured at pre (T1) and posttest (T2) using the OARS-EX and SPDSA. Scores will be compared across time point and group using mixed model ANOVA.

G4 Statistical Methods

See above. Analysis will be conducted with IBM SPSS software.

G5 Missing Outcome Data

Participants with missing data will be excluded from analyses involving those data. Since this is a small pilot study, we intend to maximise the use of data we can collect.

G6 Unblinding Procedures

NA (this is not a blinded study)

H Data Handling and Record Keeping

H1 Confidentiality and Security

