J4 Subject Stipends or Payments

Subjects will be given a check for participating in this study.

J5 Study Timetable

Recruitment will occur once the IRB is approved through approximately August 2019, and the study will begin in September 2019. This will ensure ample time for participants to consider participating in the study. Participation in this study is completely voluntary and that will be verbally told to each participant and on the written consent.

Prior to the start of the study, research team members will be trained and checked out on each assessment and the use of RedCap.

Baseline testing will occur in late August 2019, allowing the intervention to begin in September 2019 and run for the following 12 weeks until November 2019. Post testing will occur in that following week. Due to the holiday season and school schedules, the control participants will begin the second wave of intervention in January 2020 until March of 2020.

K Publication Plan

The research team plans to publish findings from this study at its completion.

L Attachments

L1 Tables

Table 1. IMPROVment® Class Components

Components	Class Description
Seated Exercise	Class begins with all participants seated in a chair. Movement cues are given to move different parts of the body in different qualities (i.e. sharp and soft). This part of class serves as a warm up for the body prior to engaging in bigger movements.
Standing Barre Work	Movement progresses from a seated position to standing while still holding onto the chair for extra support. Barre work begins to

	test balance abilities and increase level of movement executed (i.e. balancing on one leg).
Across the Floor	This is the section of class in which ID is incorporated most in several movement activities. These ID tasks are done both individually, in partners, and as a large group. Participants are not limited to staying close to their chairs and move around throughout the space using ID movement (i.e. moving in sync with another person in the room).

Table 2. IMPROVment® Class Themes

Class Themes

Class Themes	Description
Isolation	Movement of a specific body part or parts.
Shape	How the body moves as a whole, as a combination of body parts, or as individual body parts. Shape can also be impacted by other objects in the environment (i.e. chairs, walls, other participants).

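### Coin flip with a stop at 10 (2.d) has no stated timing or concealment, so late assignments can be foreseeable and, at 15 or 16 recruited, a group can fall below 7

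*Combined protocol and SAP*

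**What the plan says.** - **Order of steps.** The opening summary says "Once enrolled, participants will undergo baseline testing (T1). Then participants will be randomly assigned to one of two groups". Section 2.d repeats this order: "After consent is given and T1 testing is completed, participants will be randomly assigned (coin flip", and then names the immediate-class (ID) and wait-list (WC) groups.
- **Stop rule (2.d).** "Once we reach 10 participants in a group, remaining participants will be assigned to the other group". No section says who tosses, who keeps the running count, or whether those who take consent and test are kept unaware of it. G6 states that the study is not blinded.
- **Numbers.** Section 2.c: "Approximately 15-20 participants diagnosed with PD will be recruited for this study". E1 and G1: "Each group will have 7-10 participants, a typical size for ID classes". G1 adds "we aim to recruit 10 participants per group to ensure there are at least 7 participants in the class", which means 20 in total.
- **Timetable (J5).** "Recruitment will occur once the IRB is approved through approximately August 2019, and the study will begin in September 2019"; "Baseline testing will occur in late August 2019, allowing the intervention to begin in September 2019". There is one baseline period and one start date for the first class series.
- **Exceptions.** E1 and 2.d also let a person be placed in a group by preference or availability. How many such placements to expect is not stated.
- **Baseline questionnaires (F2).** OARS-Ex and SPDSA, the Aim 2 outcomes, may be completed at any time before the first day of intervention.

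**The concern.** Assigning after consent and T1 is meant to keep the group unknown while a person is being enrolled and measured. A stop rule weakens that protection when tosses are made one person at a time. Once a group holds 10, everyone still to come goes to the other group, and anyone who knows the count knows this in advance.

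Knowledge of the group could then affect three things: whether a borderline candidate is enrolled (severe comorbidity and contraindication to activity are not defined), what is said at consent, and how T1 is given. The Alternate Uses Task, an Aim 1 outcome, involves tester prompts and a tester's offer to stop. T1 is one half of the time-by-group comparison in G3, so a shift at baseline passes into the estimated effect.

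The rule also fails to secure the planned group size. It limits the larger group to 10 but sets no lower limit for the smaller one.

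**Working it through.** **Inputs.** Fair coin and stop at 10 (2.d); total N from 15 to 20 (2.c); aim of 10 per group, so N = 20 (G1); planned group size 7 to 10 (E1, G1). Assumption for the main figures: nobody is placed by preference or availability. The plan gives no figure of its own on this point, so there is none to reproduce.

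**Step 1: forced assignments.** An assignment is forced if a group already holds 10 when its turn comes. At least k assignments are forced if one group reaches 10 within the first N − k tosses. For N up to 20 and k of at least 1, both groups cannot do so, hence

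P(at least k forced) = 2 × P(Bin(N − k, 0.5) ≥ 10).

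Example, N = 15, k = 1: 2 × P(Bin(14, 0.5) ≥ 10) = 2 × (1001 + 364 + 91 + 14 + 1)/16384 = 0.180.

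The expected number forced is the sum of these probabilities over k from 1 to N − 10. At N = 15: 0.1796 + 0.0923 + 0.0386 + 0.0117 + 0.0020 = 0.32. At N = 20 the closed form gives 20 × C(20,10)/2^20 = 20 × 184,756/1,048,576 = 3.52.

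| N | P(at least one forced) | Expected forced |
|---|---|---|
| 15 | 18% | 0.32 |
| 16 | 30% | 0.63 |
| 17 | 45% | 1.08 |
| 18 | 63% | 1.71 |
| 19 | 81% | 2.52 |
| 20 | 100% | 3.52 |

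At N = 20 the expected share is 3.52/20 = 18%; three or more are forced with probability 63%, and five or more with probability 30%. A simulation of 200,000 runs gave 3.51 forced at N = 20 and 0.32 at N = 15.

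**Step 2: sensitivity to preference placements.** If four people are first placed in one group and count towards its 10 (an assumption), the results become 38% and 0.85 expected at N = 15, and 100% and 4.63 expected at N = 20.

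**Step 3: when forced means foreseeable.** The count in Step 1 is the same whenever the tosses are made. What differs is who can know the result, and when.

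- *Person by person:* forced assignments can be known before those people consent or are tested.
- *All after the last T1:* nothing is known before consent or T1 testing. Whoever orders the list still influences who falls in the forced tail. Questionnaires returned late under F2 could still follow assignment.

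**Step 4: group below 7.** At N = 15 only an 8:7 split keeps both groups at 7 or more: P(a group below 7) = 1 − 2 × C(15,7)/2^15 = 1 − 12,870/32,768 = 61%. At N = 16 the acceptable splits are 8:8 and 9:7 either way: 1 − (12,870 + 2 × 11,440)/65,536 = 45%. From N = 17 the stop at 10 leaves at least 7 in the other group, so the probability is 0. These figures do not depend on when the tosses are made.

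**The case against.** A reader might infer that 2.d makes the last assignments known before consent. The documents do not establish that. Both statements of the order of steps also fit tossing for the whole cohort once baseline testing is over. The ID group is to start the week after assignment, and J5 gives one late-August testing period and one September start, which suits a single assignment point. A batch of tosses has a running count too. This part of the objection stands, so the foreseeability point must be conditional. The stop rule's wording, which speaks of reaching a number and of those remaining, still leans towards rolling assignment, and J5 lets recruitment run to about August, so enrolment and testing may overlap.

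A reader might also take foreseeable assignments as certain. They are certain only at 20. At 15, under fair tossing, the stop rule forces nobody 82% of the time.

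It is tempting to add that late enrolees would meet more experienced testers. H2 and J5 require testers to be trained and checked before the study starts, which gives that argument little support. Nor do the documents show that those who consent or test see the count; they are silent on it.

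Finally, placement by preference or availability may be the larger threat to random allocation, and changing the toss does not remove it. That is correct, and any remedy has to deal with those people explicitly.

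**Conclusion.** The point holds in conditional form. Section 2.d should say when assignment happens and how it is concealed, and the coin with a stop at 10 should be replaced.

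- If tosses are made person by person, at least one assignment can be known beforehand with probability 18% at N = 15, 63% at N = 18 and 100% at N = 20, where 3.5 are expected. This assumes a fair coin, no preference placements, and a count visible to the team.
- If all tosses follow the last T1, the loss of concealment before T1 testing disappears, but the order of tossing still matters.
- Under either reading, and again with no preference placements, a group is assigned fewer than 7 with probability 61% at N = 15 and 45% at N = 16.

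The size and direction of any resulting bias cannot be derived from the documents, and none is claimed. The change is worth making because it helps under both readings and the timetable allows it.

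**What to change.** In 2.d, replace the coin and the stop rule with one computer-generated draw of fixed, near-equal group sizes.

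1. Make the draw only after every participant has completed T1 testing and all T1 questionnaires. Change F2 so that OARS-Ex and SPDSA are returned before the draw, not merely before the first class.
2. File the resulting list before anyone is told a group.
3. Before the draw, identify and record anyone placed by preference or availability. Keep them out of the draw and report them separately from the randomised comparison.
4. Set the draw sizes so that neither group exceeds 10 once placed people are counted. With none placed, the split is 10:10 at N = 20 and 8:7 at N = 15, so both groups hold at least 7. If, for illustration, four of 20 were placed in one group, the other 16 would be drawn 6:10 (10 − 4 = 6), so the limit takes precedence over equality.

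No assignment made by the draw can then be known before consent or T1, at any N from 15 to 20.

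**Cost.** A rewritten paragraph in 2.d and a sentence in F2. Participants learn their group somewhat later, shortly before the September start, which matters because E1 recognises scheduling difficulties. Questionnaires must also be chased before the draw.

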This is quasi-randomized wait-list controlled trial. Once enrolled, participants will undergo T1 assessments consisting of the primary outcome measures for each aim (described above and attached) and other relevant factors (e.g. demographics, clinical characteristics, motor function). Participants will be randomly assigned (coin flip) to one of two groups: ID or WC group. Although our aim is to randomize participants to the different groups, if someone has a strong preference or inability to participate in one group or the other due to scheduling issues, we will try to accommodate his/her preferences. Each group will have 7-10 participants, a typical size for ID classes. This ensures enough participants to create a cohesive group, but also to provide an appropriate level of safety. The ID group will participate in a 12-week intervention where the group will meet once a week for a 1-hour IMPROVment® class. Participants in the WC group will continue with their regular routine for 12 weeks. After 12 weeks, all participants will complete T2 testing. Then WC participants will participate in the same IMPROVment® method for the following 12 weeks followed by T3 testing.

E2 Subject Selection and Withdrawal

2.a Inclusion Criteria

Inclusion criteria for this study include over 50 years old, PD diagnosis with Hoehn and Yahr stage 1-3 (mild to moderate), independently walks at least 3 meters and ability to comprehend and follow simple verbal cues.

2.a Exclusion Criteria

Exclusion criteria of this study include, a Montreal Cognitive Assessment score less than or equal to 21 (indicating cognitive impairment that may interfere with class participation), diagnosis of other severe comorbidities, and contraindications to physical activity. In addition, participants must attend at least ten of the twelve classes for their data to be included in analysis (they will still be allowed to participate in the classes).

2.b Ethical Considerations

Participants will be given the choice to be involved in the study and may withdraw at any time without penalty.

2.c Subject Recruitment Plans and Consent Process

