Participants may withdraw from this study at any time. To withdraw, participants will tell a member of the study team that he/she is no longer interested in participating in the study. He/she may withdraw completely from the dance classes or continue to dance and just withdraw from testing.

2.g Data Collection and Follow-up for Withdrawn Subjects

Data already collected on participants who withdraw from the study will be securely stored in a RedCap database. With the participants' consent, they may be used for comparison to those who remain in the study or for description of those who withdraw. If a participant would like to withdraw their data, they will be equipped with the procedure to follow on the Human Research Protocol Office website.

E3 Study Drug

NA

F Study Procedures

F1 Screening for Eligibility

Participants will be screened for eligibility using the “Inclusion/Exclusion Criteria Referral Form: IMPROVment® Class Participation” (Appendix 1)

F2 Schedule of Measurements

T1 testing will include the collection of demographics information, National Institute of Health Toolbox Cognitive Battery, the Weekly Calendar Planning Activity, Alternate Uses Task, and the Unified Parkinson's Disease Rating Scale Section 3 Motor exam.

Participants will also be asked to complete the Older Americans Resources and Services scale, Satisfaction with Participation in Discretionary Social Activities scale, the Parkinson Anxiety Scale, the Sleep Disturbance Scale, the Parkinson's Disease Fatigue Scale and the Depression Scale questionnaires. These questionnaires can be completed prior to the first day of intervention via RedCap survey mode or on paper if preferred. In addition, participants will be asked to complete a brief mood questionnaire at the beginning and end of each class. The participant will mark how they are feeling on 4 scales (see Appendix 4).

After the first 12 week period of intervention, both groups will be invited back to complete those same assessments (T2). After the second 12 week period, only the WC group will T3 testing with the same assessments.

F3 Class Structure

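### Sections 2.f and 2.g do not assure T2 follow-up of ID participants who stop the classes, and they need reconciling with E1 and F2, which put T2 on everyone

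*Combined protocol and SAP*

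**What the plan says.** Section E2 2.f has a participant withdraw by declaring it: "participants will tell a member of the study team that he/she is no longer interested in participating in the study". It then names two routes: "He/she may withdraw completely from the dance classes or continue to dance and just withdraw from testing".

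Section 2.g, whose title promises follow-up of withdrawn subjects, deals with what is already in hand: "Data already collected on participants who withdraw from the study will be securely stored in a RedCap database". With consent, those data may be used to describe leavers or compare them with participants who remain. No later visit is mentioned.

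On who is tested at T2, E1 is general: "After 12 weeks, all participants will complete T2 testing". The opening abstract says the same and labels T2 the primary endpoint. F2 invites both groups back. None of the three makes T2 depend on attendance.

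Three other passages bear on the point:

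- The WC group keeps its usual routine until T2 and dances only afterwards (E1).
- Data enter the analysis only for participants who attended 10 or more of the 12 classes (E2, exclusion criteria).
- Participants with missing data drop out of the analyses concerned (G5).

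On losses, G1 says: "Although attrition is not anticipated, we aim to recruit 10 participants per group to ensure there are at least 7 participants in the class".

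**The concern.** The scores at risk are the ones that a comparison of the groups as assigned depends on. Section 2.f lets someone keep the class and drop the measurement, but does not name the reverse. It treats leaving as loss of interest in the study, and 2.g plans nothing further. Staff applying these two sections could reasonably treat an ID participant who gives up the classes as withdrawn and never arrange T2.

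People who leave a movement class early, whether from fatigue, worsening disease or dislike of the class, may well change differently from those who stay. Before T2 this route of loss exists only in the ID group. If those scores are not collected, the ID result at T2 describes people who tolerated the class, and no later analysis can recover the missing values. G1 intends the data to inform the power of future studies, so a distorted estimate could carry forward.

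**Working it through.** The plan gives no power, alpha, effect size, SD or expected drop-out rate, so there is no stated figure to reproduce. The check is a reading of the passages, followed by an illustration of scale.

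**Passages side by side**

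| Question | 2.f and 2.g | Abstract, E1, F2 |
|---|---|---|
| May a participant keep dancing and drop testing? | Yes, named | Not addressed |
| May a participant stop dancing and stay for T2? | Not named; not ruled out | Implied, since T2 is for all |
| Is a visit planned after withdrawal? | None described | T2 carries no attendance condition |

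The first route in 2.f refers to the classes and does not say that testing ends. But the sentence before it frames withdrawal as leaving the study, and 2.g is silent on later visits. Both readings are open, so T2 for a class-leaver is neither excluded nor secured.

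**Asymmetry.** ID has classes between T1 and T2 and WC has none. Leaving the class before T2 can therefore occur only in ID. Withdrawal for other reasons can occur in both groups.

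**Illustration of scale**

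1. Losses tolerated, from G1: 1 - 7/10 = 0.30, or up to 3 of 10. This is a margin for class size, not a forecast of lost T2 scores.
2. Let stayers' mean change be S and leavers' be S - D. With k leavers of 10, the mean over all assigned is [(10 - k)S + k(S - D)]/10 = S - (k/10)D. Using stayers only overstates it by (k/10) x D.
3. D is assumed to be 0.25 to 1.0 SD; neither its size nor its direction is in the documents.

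| k of 10 | D = 0.25 | D = 0.5 | D = 1.0 |
|---|---|---|---|
| 1 | 0.025 | 0.05 | 0.10 |
| 2 | 0.05 | 0.10 | 0.20 |
| 3 | 0.075 | 0.15 | 0.30 |

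With two time points, the group-by-time contrast is the difference in mean change. If WC is unaffected, the shift passes to that contrast in full.

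**Precision.** For a two-sample t test of change (noncentral t, two-sided alpha 0.05 and standardised difference d assumed), going from 10 v 10 to 7 v 10 lowers power from 0.185 to 0.158 at d = 0.5, from 0.395 to 0.330 at d = 0.8, and from 0.562 to 0.476 at d = 1.0. The larger worry is one-sided selection.

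**Link to the attendance rule.** A participant who leaves before the tenth class is outside the planned analysis even if measured at T2. The shift in the table would then arise from that rule alone. Collecting T2 is necessary to remove it, but not sufficient.

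**The case against.** A reader might infer from 2.f that ID class-leavers have no primary-endpoint measurement. The documents do not say so. The first route is withdrawal from the classes, and testing is named only in the second. The first route can therefore be read as the very option that seems to be missing. The abstract, E1 and F2 also assign T2 without regard to attendance. This objection stands: the text supports follow-up that is not assured, and nothing stronger.

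A reader might also infer that the WC result at T2 would come from everyone. It need not, because any participant may withdraw at any time. What stands is narrower: WC has no class to leave before T2, and net loss by group is unknown.

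The weightiest objection is that changing 2.f alone would barely alter the planned analysis, because the 10-of-12 rule already excludes most class-leavers. That is right, and the fix has to cover the analysis too. It does not remove the point, since an analysis rule can be revised or supplemented later while an uncollected score cannot be recovered.

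Finally, this is a pilot of 15 to 20 people that accommodates group preferences. An as-assigned comparison would not be a fully randomised one, and attrition is not anticipated. These facts limit the point's importance. Consent pages are not available, so any withdrawal wording there cannot be judged.

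**Conclusion.** The point holds as a gap and inconsistency in the withdrawal rules. Section 2.f does not expressly offer stopping classes while remaining for T2, 2.g provides no follow-up after withdrawal, and the abstract, E1 and F2 put T2 on all participants. Follow-up of ID class-leavers at the primary endpoint is therefore not assured, and this route of loss has no counterpart in WC before T2.

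Its size in this trial is unknown. The range of about 0.03 to 0.30 SD is illustrative and rests on 1 to 3 leavers of 10 and an assumed D of 0.25 to 1.0 SD in the unfavourable direction. It should not be read as a bias caused by 2.f alone or added to that from the attendance rule, because largely the same people are affected. The change is worth making because it is cheap and lost scores cannot be recovered, but it affects the results only if the scores are also analysed.

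**What to change.** - In 2.f, separate leaving the classes from leaving the study, and name stopping classes while remaining for testing as an option.
- In 2.g, state that anyone who stops classes is still invited to T2, or at least to the REDCap questionnaires, unless they decline testing. This brings both sections into line with E1 and F2.
- Record the date and reason for stopping classes.
- In G3, add a T1-T2 comparison by assigned group that includes these scores whatever the attendance, since the 10-of-12 rule would otherwise exclude them. State also how that rule applies to WC in the T1-T2 comparison, because WC classes come after T2.

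The cost is protocol wording, matching consent wording where needed, and one further analysis. E1 already plans T2 for all participants, so no new visit is created. Some class-leavers will decline, so the gap will narrow without closing, and the ID estimate may be slightly less favourable.
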